3 HYPOTHESES, OBJECTIVES, AND ENDPOINTS

Hypotheses are aligned with objectives in the Objectives and Endpoints table.

The following objectives and endpoints will be evaluated in Japanese males, 16 to 26 years of age.

Primary Objective	Primary Endpoint
Objective: To demonstrate that a 3-dose regimen of the 9vHPV vaccine will reduce the combined incidence of HPV 6/11/16/18-related anogenital (external genital and intra-anal) persistent infection detected in samples from two or more consecutive visits 6 months (± 1-month window) or longer apart compared with placebo in participants who are seronegative at Day 1 and PCR-negative Day 1 through Month 7 to the relevant HPV type.	HPV 6/11/16/18-related anogenital persistent infection
Hypothesis: Administration of a 3-dose regimen of the 9vHPV vaccine reduces the combined incidence of HPV 6/11/16/18-related anogenital persistent infection detected in samples from two or more consecutive visits 6 months (± 1-month window) or longer apart compared with placebo (The statistical criterion for success requires that the lower bound of the 2-sided 95% CI of vaccine efficacy is >0%).	
Objective: To evaluate the safety and tolerability of the 9vHPV vaccine.	-Solicited injection-site adverse events (AEs) -Systemic AEs -Serious adverse events (SAEs)

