• HPV 6/11/16/18/31/33/45/52/58-related anogenital persistent infection detected in samples from three or more consecutive visits 6 months (± 1-month window) or longer apart (i.e., at least 12 months persistent infection)

These endpoints will be also evaluated for each HPV types.

9.4.2 **Immunogenicity Endpoints**

GMT to each of HPV 6, 11, 16, 18, 31, 33, 45, 52, and 58 at 1 month post last dose (Month 7) based on cLIA using serum samples.

Seroconversion to each of HPV 6, 11, 16, 18, 31, 33, 45, 52, and 58 at 1 month post last dose (Month 7) based on cLIA using serum samples. Seroconversion is defined as changing a participant's serostatus from seronegative at Day 1 to seropositive at 1 month post last dose (Month 7). A participant with anti-HPV cLIA titer at or above the serostatus cutoff of the cLIA for a given HPV type is considered seropositive for that HPV type.

9.4.3 **Safety Endpoints**

- Solicited injection-site AEs and elevated temperatures during Days 1 through 5 postvaccination
- Systemic AEs and SAEs during Days 1 through 15 postvaccination
- Serious vaccine-related AEs observed any time during the study

9.5 **Analysis Populations**

In efficacy and immunogenicity analysis populations, participants are analyzed in the vaccination group to which they were randomized (i.e., as-randomized). In safety analysis population, participants are analyzed according to the vaccination regimen actually received (i.e., as-treated).

9.5.1 **Efficacy Analysis Populations**

Per-Protocol Efficacy (PPE) Population

The PPE population will serve as the primary population for the analysis of efficacy in this study. To be included in the per-protocol population, participants must:

- 1. Have received all 3 vaccinations with the correct dose of the correct clinical material within 1 year.
- 2. Have Month 7 swab samples collected within 14 to 72 days post dose 3 with non-missing PCR result.

- 3. Be seronegative to the appropriate HPV type(s) at baseline and PCR-negative to the appropriate HPV type(s) on all swabs and biopsies (if collected) from baseline through Month 7.
- 4. Have no other protocol violations that could interfere with the evaluation of efficacy.

The final determination on protocol violations, which will be used for determining the PPE population, will be made prior to the database lock and will be documented in a separate memo or the sSAP.

HPV Type-Specific Naïve (HN-TS) Population

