9.6.3 Statistical Methods for Safety Analyses

Safety and tolerability will be assessed by clinical review of all relevant parameters including AEs and postvaccination temperature measurements. The analysis of safety results will follow a tiered approach (Table 7). The tiers differ with respect to the analyses that will be performed. AEs (specific terms as well as system organ class terms) are either pre-specified as "Tier 1" endpoints or will be classified as belonging to "Tier 2" or "Tier 3" based on the observed proportions of participants with an event. The safety analysis strategy is summarized in Table 7.

Tier 1 Events

Safety parameters or AEs of special interest that are identified a priori constitute "Tier 1" safety endpoints that will be subject to inferential testing for statistical significance. There are no Tier 1 events for this protocol based on the global safety data on the 9vHPV vaccine.

Tier 2 Events

Tier 2 parameters will be assessed via point estimates with corresponding 95% CIs provided for the differences in the proportion of participants with events (using the Miettinen and Nurminen method [Miettinen, O. and Nurminen, M. 1985]). Membership in Tier 2 requires that at least 1% of participants in any treatment group exhibit the event.

In addition to individual events that occur in at least 1% of participants in any treatment group, the broad AE categories consisting of the proportion of participants with SAEs during

Days 1 through 15 postvaccination, vaccine-related SAEs observed any time during the study, and elevated temperatures (≥37.5°C) will be considered Tier 2 endpoints. The proportion of participants with solicited injection-site AEs (pain/tenderness, swelling, and redness) and severe injection-site AEs during Days 1 through 5 postvaccination will also be included in Tier 2 endpoints. Detailed endpoints and day ranges are summarized in Table 7.

Tier 3 Events

Safety endpoints that are not Tier 1 or 2 events are considered Tier 3 events. Only point estimates (counts and percentages) by vaccination group are provided for Tier 3 safety parameters. Safety analyses will be based on the observed data (i.e., with no imputation of missing data).

Table 7 Analysis Strategy for Safety Parameters

Safety Tier	Safety Endpoint (a)	95% CI for Comparison of 9vHPV to Placebo	Descriptive Statistics
Tier 2	Injection-site pain/tenderness, swelling, and redness during Days 1 through 5 postvaccination	X	X

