	Other injection-site AEs (incidence ≥1% of participants in either group) during Days 1 through 5 postvaccination	X	X
	Severe injection-site AEs (b) during Days 1 through 5 postvaccination	X	X
	Systemic AEs (incidence ≥1% of participants in either group) during Days 1 through 15 postvaccination	X	X
	Elevated temperatures (c) during Days 1 through 5 postvaccination	X	X
	SAEs during Days 1 through 15 postvaccination	X	X
	Serious vaccine-related AEs observed any time during the study	X	X
Tier 3	AEs by SOC		X
	Maximum intensity rating for each category of injection- site AEs		X
	Maximum intensity rating, over all systemic AEs		X
	Maximum temperatures		X
	New medical conditions		X

Abbreviations: AE=adverse event, SAE=serious adverse event, SOC=System Organ Class

- (a) The day of vaccination is counted as Day 1. Day ranges for endpoints are as follows: injection-site AEs and maximum temperatures Days 1 through 5 postvaccination; systemic AEs Days 1 through 15 postvaccination.
- (b) For the injection-site redness and swelling 0 to 2.5 cm (0 to 1 inch) will be categorized as mild, >2.5 to 5 cm (>1 inch to 2 inches) will be categorized as moderate, and >5 cm (>2 inches) will be categorized as severe.
- (c) Defined as maximum (over the follow-up period) temperature $\ge 37.5^{\circ}$ C.

Note: X = indicated summary statistic will be provided.

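### Table 7 plans no confidence interval against placebo for any systemic AE or for severe systemic AEs pooled over terms, although systemic AEs are a primary safety endpoint and severe injection-site AEs get one

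*Combined protocol and SAP*

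**What the plan says.** Section 3 places the safety objective, "To evaluate the safety and tolerability of the 9vHPV vaccine", among the primary objectives and gives it three endpoints: "Solicited injection-site adverse events (AEs) -Systemic AEs -Serious adverse events (SAEs". It states no safety hypothesis. Section 9.4.3 sets the window: "Systemic AEs and SAEs during Days 1 through 15 postvaccination".

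Section 9.6.3 names no Tier 1 events, so no safety endpoint is tested. A Tier 2 item gets a Miettinen-Nurminen 95% CI for the difference in proportions. Anything outside Tiers 1 and 2 is Tier 3 and gets counts and percentages by group.

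Items enter Tier 2 in two ways. Individual events enter if at least 1% of either arm has them. Certain items enter by name, introduced as "the broad AE categories consisting of the proportion of participants with SAEs during" Days 1 through 15, followed by vaccine-related SAEs and elevated temperature; the next sentence adds solicited and severe injection-site AEs. Neither any systemic AE nor severe systemic AE is named.

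Table 7 follows this. Its Tier 2 rows include "Systemic AEs (incidence ≥1% of participants in either group) during Days 1 through 15 postvaccination" and "Severe injection-site AEs (b) during Days 1 through 5 postvaccination". Systemic intensity appears only in Tier 3, as "Maximum intensity rating, over all systemic AEs".

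**The concern.** Two of the three primary safety endpoints, solicited injection-site AEs and SAEs, have a Tier 2 row with no incidence threshold. The only Tier 2 row for the third, systemic AEs, carries the 1% filter. Severity is also handled unevenly: a severe injection-site reaction (for redness or swelling, above 5 cm) counts towards a planned comparison with placebo. Severe systemic AEs as a group, which Section 10.3.5 defines by their stopping normal daily activities, do not.

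If severe systemic events were scattered over many terms, each could stay below 1% while the total differed between arms. The plan would then show two percentages side by side and no measure of uncertainty for their difference. An interval calculated after unblinding could be criticised as selected.

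**Working it through.** **Inputs.** Section 9.9.3 uses 525 vaccinees; 1:1 randomization of about 1050 participants gives the same number on placebo. The 1% rule and the CI method come from Section 9.6.3. The documents give no systemic AE rate, so every event count below is an assumption.

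**The plan's own safety figures.** With 525 vaccinees and a 0.5% SAE incidence, the chance of at least one SAE is 1 - 0.995^525 = 92.8%; the plan states 93%. With no events, the one-sided 95% upper bound is 1 - 0.05^(1/525) = 0.57%; the plan states <0.6%. Both reproduce, and this point disputes no number in the plan.

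**Where each summary falls.**

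| Summary | Placement | 95% CI vs placebo |
|---|---|---|
| Solicited injection-site AEs | Tier 2, named | Yes |
| Severe injection-site AEs | Tier 2, named | Yes |
| SAEs, Days 1-15 | Tier 2, named | Yes |
| Elevated temperature | Tier 2, named | Yes |
| Systemic AEs at 1% or more | Tier 2, by threshold | Yes |
| Systemic AEs by maximum intensity | Tier 3, explicit row | No |
| Any systemic AE | No row; Tier 3 by default | No |

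**The threshold in participants.** 0.01 × 525 = 5.25, so a term needs at least 6 participants in one arm. (With 500 or fewer in an arm's safety population, 5 would be enough.)

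**What the missing intervals would look like.** The Miettinen-Nurminen limits are the values d at which (p1 - p2 - d)/√V(d) = ±1.96. Here V(d) = [r1(1-r1)/n1 + r2(1-r2)/n2] × N/(N-1), N = n1 + n2, and r1, r2 are the maximum-likelihood proportions constrained to r1 - r2 = d. With n1 = n2 = 525:

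| Assumed counts, vaccine vs placebo | Percentages | Difference, points | 95% CI |
|---|---|---|---|
| Severe systemic AE, 10 vs 2 | 1.9 vs 0.4 | 1.5 | 0.3 to 3.1 |
| Severe systemic AE, 10 vs 3 | 1.9 vs 0.6 | 1.3 | -0.01 to 3.0 |
| Any systemic AE, 131 vs 100 | 25.0 vs 19.0 | 5.9 | 0.9 to 10.9 |
| Any systemic AE, 126 vs 105 | 24.0 vs 20.0 | 4.0 | -1.0 to 9.0 |

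One more placebo participant with a severe event moves the first interval from excluding 0 to just including it. The rows show the precision available at this sample size; they do not predict a result.

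**The case against.** The strongest reply is that nothing here is an error. The safety objective has no hypothesis, systemic AEs do receive a placebo comparison in Tier 2, and the plan nowhere promises a pooled interval. That stands: this is a reporting improvement.

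Several narrower replies also stand, wholly or in part:

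- A reader might infer that all-systemic and severe systemic AEs are reported as bare counts with no view of the comparison. Tier 3 gives percentages for both arms, so the difference follows by subtraction and anyone can compute an interval. What is missing is the prespecified interval.
- A reader might infer that no severe systemic event contributes to any interval. In fact a serious event enters the SAE row, a fever enters the elevated-temperature row, and any event in a term at or above 1% counts in that term's CI.
- The asymmetry is limited. The intensity distribution of injection-site AEs is also Tier 3, and Table 7 has no row for any injection-site AE either. Only the severe injection-site row has no systemic counterpart. Severe redness and swelling are judged by size while systemic intensity is rated by the investigator, which may explain the choice, but the plan does not say so.
- The term-by-term reading is an inference, because the Tier 2 systemic row does not itself say term. Section 9.6.3 supports the inference by separating individual events from categories admitted by name. If the row was meant as the pooled total, the any-systemic-AE gap closes but the severe one remains, because its Tier 3 placement is explicit.

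Two replies do not close the gap. The SAE row does not cover severe events in general, since Section 10.3.5 warns against confusing severe with serious. The supplemental SAP is not among the documents. Section 9 gives it changes to exploratory and other non-confirmatory analyses, so it might add such output, but nothing supplied shows that it does.

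**Conclusion.** The point holds as a modest gap in the safety tables. One endpoint of the primary safety objective has a planned interval against placebo only for events at or above 1%. Its pooled total and its severe subset have descriptive percentages only.

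The practical loss is mainly the pooled total, plus non-serious, non-febrile severe systemic events in terms with fewer than 6 of 525 participants. How much would fall there is unknown, because the documents give neither systemic AE rates nor their spread over terms.

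The stronger inference, that a real excess would go unseen or that the safety conclusion is invalid, is not supported. Percentages by arm are planned, safety is also assessed by clinical review, and under the assumed counts the interval may or may not exclude 0. Efficacy, sample size and data collection are unaffected.

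**What to change.** In Section 9.6.3 and Table 7, add two Tier 2 rows for Days 1 through 15 after vaccination: the proportion of participants with at least one systemic AE, and the proportion with at least one severe systemic AE (maximum intensity severe, graded as in Section 10.3.5). Give each the Miettinen-Nurminen 95% CI regardless of the 1% threshold. Keep the Tier 3 maximum-intensity row as the descriptive breakdown, and state that the existing Tier 2 systemic row refers to individual terms, if that is the intent.

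The data are already collected and the method is already planned. The downside is two more intervals without multiplicity adjustment, as for the other Tier 2 intervals. Under the opening rule of Section 9, a non-confirmatory change of this kind can go into the supplemental SAP before unblinding. If unblinding has already taken place, the rows should be identified as post hoc in the study report.

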9.6.4 Summaries of Baseline Characteristics, Demographics, and Other Analyses

Baseline characteristics and demographic variables

Baseline and demographic characteristics; prior and concomitant therapies; counts and percent of participants screened, enrolled, vaccinated and the primary reason for discontinuation; will be summarized in tabular format by vaccine group. No statistical hypothesis tests will be performed on these characteristics.

9.7 Interim Analyses

No interim analyses are planned in this study.

9.8 Multiplicity

The overall type 1 error rate associated with testing the primary and secondary efficacy hypotheses will be controlled by a fixed sequence procedure. When at least 17 cases of the primary endpoint and at least 17 cases of the secondary endpoint have been observed, the primary efficacy hypothesis will be tested at a 1-sided type 1 error rate ≤ 0.025 , as discussed in Section 9.9.1. The secondary efficacy hypothesis will be tested at a 1-sided type 1 error rate ≤ 0.025 only if the primary efficacy hypothesis is successfully demonstrated.

9.9 Sample Size and Power Calculations

This is an event-driven study and the planned sample size is approximately 1050 participants.

9.9.1 Sample Size and Power for Testing the Primary Efficacy Hypothesis

With a 1:1 randomization between the 2 arms, the decision rule displayed in Table 8 for testing the primary efficacy hypothesis of VE >0% at a total of 17 cases will have 1-sided type 1 error rate ≤ 0.025 and power has 94% if the true VE is at least 85% (see Table 8). Type 1 error rate and power calculations were done based on the method proposed by Chan and Bohidar (1998) [Chan, I. S. F. and Bohidar, N. R. 1998]. Table 8 also displays the decision rule that will be used if the primary efficacy hypothesis is tested with total cases greater than 17.

Table 8 Decision Rule and Corresponding Type 1 Error rate and Power for Testing the Primary Efficacy Hypothesis

		Critical C	Case Split						
						True Vacc	ine Efficac	y (VE)	
Analysis Time	Total			Type 1 Error	75%	80%	85%	90%	95%
Point	Cases	Vaccine	Placebo	rate		Po	ower (%)		
Final	17	4	13	0.0245	76	86	94	98	>99
	18	4	14	0.0154	72	83	92	98	>99
	19	4	15	0.0096	67	80	91	98	>99
	20	5	15	0.0207	80	90	96	99	>99
	21	5	16	0.0133	77	88	95	99	>99
	22	5	17	0.0085	73	85	94	99	>99
	23	6	17	0.0173	84	93	98	>99	>99
	24	6	18	0.0113	81	91	97	>99	>99
	25	7	18	0.0216	89	96	99	>99	>99

A total of approximately 1050 participants are needed to be enrolled in order to accumulate approximately 17 total primary endpoint cases within 56 months from the time the first study participant signs the ICF based on the following assumptions. Assumption is based on V501-122:

- 14 months enrollment;
- Exclusion rate from PPE analysis is approximately 15%;
- Attrition rate is approximately 5% per year;
- Annual incidence rate for the primary efficacy endpoint is 1.9% per year;
- True VE is 85%.

9.9.2 Sample Size and Power for Testing the Secondary Efficacy Hypothesis

Table 8 also displays the decision rule that will be used for testing the secondary efficacy hypothesis with 17 or more total cases. The testing of the secondary efficacy hypothesis of VE >0% at 17 total cases will have 1-sided type 1 error rate \leq 0.025 and power has 94% if the true VE is at least 85% (see Table 8).

A total of approximately 1050 participants are needed to be enrolled in order to accumulate at least 17 total secondary endpoint cases at the time of accumulation of at least 17 primary efficacy cases, i.e., within 56 months from the time the first study participant signs the ICF, when the annual incidence rate of the secondary efficacy endpoint is 2.0% per year and true VE is equal to 85% (based on the same enrollment duration, attrition, and exclusions from the PPE population assumed in Section 9.9.1.

9.9.3 Sample Size and Power for Safety Analysis

The probability of observing at least one SAE in this study depends on the number of participants vaccinated and the underlying percentage of participants with SAE in the study population. If the underlying incidence of SAE is 0.5%, there is a 93% chance of observing at least one SAE among 525 participants in the 9vHPV vaccine group. If no adverse experiences are observed among the 525 participants in the 9vHPV vaccine group, this study will provide 95% confidence that the underlying percentage of participants with an SAE is <0.6%.

9.10 Subgroup Analyses

To determine whether the treatment effect is consistent across various subgroups, the point and 95% CI estimates of VE for the primary, the secondary efficacy and the exploratory endpoint will be provided by Age, Sexual Orientation, Smoking, Lifetime Sexual Partners, Presence of Other HPV Types.

Both for HM and MSM subgroups analyses will be performed for following endpoints.

Efficacy:

- HPV 6/11/16/18-related anogenital persistent infection detected in samples from two or more consecutive visits 6 months (± 1-month window) or longer apart
- HPV 31/33/45/52/58-related anogenital persistent infection detected in samples from two or more consecutive visits 6 months (± 1-month window) or longer apart
- HPV 6/11/16/18/31/33/45/52/58-related anogenital persistent infection detected in samples from two or more consecutive visits 6 months (± 1-month window) or longer apart
- HPV 6/11/16/18/31/33/45/52/58-related genital warts, PIN, penile, perianal or perineal cancer
- HPV 6/11/16/18/31/33/45/52/58-related intra-anal persistent infection detected in samples from two or more consecutive visits 6 months (± 1-month window) or longer apart
- HPV 6/11/16/18/31/33/45/52/58-related anogenital persistent infection detected in samples from three or more consecutive visits 6 months (± 1-month window) or longer apart (i.e., at least 12 months persistent infection)

Immunogenicity:

- GMT to each of HPV 6, 11, 16, 18, 31, 33, 45, 52, and 58 at Month 7
- Seroconversion to each of HPV 6, 11, 16, 18, 31, 33, 45, 52, and 58 at Month 7

9.11 Compliance (Medication Adherence)

Compliance in this study is defined as receipt of all 3 doses of the 9vHPV vaccine. To summarize compliance, the numbers of participants who receive each vaccination will be tabulated. For each of doses 2 and 3, histograms of the time (in weeks) of administration of the vaccine relative to the target vaccination visit will be provided.

9.12 Extent of Exposure

The extent of exposure will be summarized by the number and proportion of randomized participants administered the 9vHPV or placebo.

94

SUPPORTING DOCUMENTATION AND OPERATIONAL CONSIDERATIONS

10.1 Appendix 1: Regulatory, Ethical, and Study Oversight Considerations

10.1.1 **Code of Conduct for Clinical Trials**

Merck Sharp & Dohme LLC, Rahway, NJ, USA (MSD)

Code of Conduct for Interventional Clinical Trials

I. Introduction

A. Purpose

MSD, through its subsidiaries, conducts clinical trials worldwide to evaluate the safety and effectiveness of our products. As such, we are committed to designing, implementing, conducting, analyzing, and reporting these trials in compliance with the highest ethical and scientific standards. Protection of participants in clinical trials is the overriding concern in the design and conduct of clinical trials. In all cases, MSD clinical trials will be conducted in compliance with local and/or national regulations (including all applicable data protection laws and regulations), and International Council for Harmonisation Good Clinical Practice (ICH-GCP), and also in accordance with the ethical principles that have their origin in the Declaration of Helsinki.

B. Scope

Highest ethical and scientific standards shall be endorsed for all clinical interventional investigations sponsored by MSD irrespective of the party (parties) employed for their execution (e.g., contract research organizations, collaborative research efforts). This Code is not intended to apply to trials that are observational in nature, or which are retrospective. Further, this Code does not apply to investigator-initiated trials, which are not under the full control of MSD.

II. Scientific Issues

A. Trial Conduct

1. Trial Design

Except for pilot or estimation trials, clinical trial protocols will be hypothesis-driven to assess safety, efficacy and/or pharmacokinetic or pharmacodynamic indices of MSD or comparator products. Alternatively, MSD may conduct outcomes research trials, trials to assess or validate various endpoint measures, or trials to determine patient preferences, etc.

The design (i.e., participant population, duration, statistical power) must be adequate to address the specific purpose of the trial and shall respect the data protection rights of all participants, trial site staff and, where applicable, third parties. All trial protocols are and will be assessed for the need and capability to enroll underrepresented groups. Participants must meet protocol entry criteria to be enrolled in the trial.

2. Site Selection

MSD's clinical trials are conducted globally in many different countries and in diverse populations, including people of varying age, race, ethnicity, gender, and accounting for other potential disease related factors. MSD selects investigative sites based on medical expertise, access to appropriate participants, adequacy of facilities and staff, previous performance in clinical trials, as well as budgetary considerations. Prior to trial initiation, sites are evaluated by MSD personnel (or individuals acting on behalf of MSD) to assess the ability to successfully conduct the trial.

Where appropriate, and in accordance with regulatory authority guidance, MSD will make concerted efforts to raise awareness of clinical trial opportunities in various communities. MSD will seek to engage underrepresented groups and those disproportionately impacted by the disease under study. MSD will

PRODUCT: V503 95

support clinical trial investigators to enroll underrepresented groups and expand access to those who will ultimately use the products under investigation.

3. Site Monitoring/Scientific Integrity

Investigative trial sites are monitored to assess compliance with the trial protocol and Good Clinical Practice (GCP). MSD reviews clinical data for accuracy, completeness, and consistency. Data are verified versus source documentation according to standard operating procedures. Per MSD policies and procedures, if potential fraud, scientific/research misconduct, privacy incidents/breaches or Clinical Trial-related Significant Quality Issues are reported, such matters are investigated. When necessary, appropriate corrective and/or preventative actions are defined and regulatory authorities and/or ethics review committees are notified.

B. Publication and Authorship

Regardless of trial outcome, MSD commits to publish the primary and secondary results of its registered trials of marketed products in which treatment is assigned, according to the pre-specified plans for data analysis. To the extent scientifically appropriate, MSD seeks to publish the results of other analyses it conducts that are important to patients, physicians, and payers. Some early phase or pilot trials are intended to be hypothesis-generating rather than hypothesis testing; in such cases, publication of results may not be appropriate since the trial may be underpowered and the analyses complicated by statistical issues such as multiplicity.

MSD's policy on authorship is consistent with the recommendations published by the International Committee of Medical Journal Editors (ICMJE). In summary, authorship should reflect significant contribution to the design and conduct of the trial, performance or interpretation of the analysis, and/or writing of the manuscript. All named authors must be able to defend the trial results and conclusions. MSD funding of a trial will be acknowledged in publications.

III. Participant Protection

A. Regulatory Authority and Ethics Committee Review (Institutional Review Board [IRB]/Independent Ethics Committee [IEC])

All protocols and protocol amendments will be submitted by MSD for regulatory authority acceptance/authorization prior to implementation of the trial or amendment, in compliance with local and/or national regulations.

The protocol, protocol amendment(s), informed consent form, investigator's brochure, and other relevant trial documents must be reviewed and approved by an IRB/IEC before being implemented at each site, in compliance with local and/or national regulations. Changes to the protocol that are required urgently to eliminate an immediate hazard and to protect participant safety may be enacted in anticipation of ethics committee approval. MSD will inform regulatory authorities of such new measures to protect participant safety, in compliance with local and/or national regulations.

B. Safety

The guiding principle in decision-making in clinical trials is that participant welfare is of primary importance. Potential participants will be informed of the risks and benefits of, as well as alternatives to, trial participation. At a minimum, trial designs will take into account the local standard of care.

All participation in MSD clinical trials is voluntary. Participants enter the trial only after informed consent is obtained. Participants may withdraw from an MSD trial at any time, without any influence on their access to, or receipt of, medical care that may otherwise be available to them.

C. Confidentiality

MSD is committed to safeguarding participant confidentiality, to the greatest extent possible, as well as all applicable data protection rights. Unless required by law, only the investigator, Sponsor (or individuals acting on behalf of MSD), ethics committee, and/or regulatory authorities will have access to confidential medical records that might identify the participant by name.

PRODUCT: V503 96

D. Genomic Research

Genomic research will only be conducted in accordance with a protocol and informed consent authorized by an ethics committee.

IV. Financial Considerations

A. Payments to Investigators

Clinical trials are time- and labor-intensive. It is MSD's policy to compensate investigators (or the sponsoring institution) in a fair manner for the work performed in support of MSD trials. MSD does not pay incentives to enroll participants in its trials. However, when enrollment is particularly challenging, additional payments may be made to compensate for the time spent in extra recruiting efforts.

MSD does not pay for participant referrals. However, MSD may compensate referring physicians for time spent on review and medical evaluation to identify potentially eligible participants.

B. Clinical Research Funding

Informed consent forms will disclose that the trial is sponsored by MSD, and that the investigator or sponsoring institution is being paid or provided a grant for performing the trial. However, the local ethics committee may wish to alter the wording of the disclosure statement to be consistent with financial practices at that institution. As noted above, all publications resulting from MSD trials will indicate MSD as a source of funding.

C. Funding for Travel and Other Requests

Funding of travel by investigators and support staff (e.g., to scientific meetings, investigator meetings, etc.) will be consistent with local guidelines and practices.

V. Investigator Commitment

Investigators will be expected to review MSD's Code of Conduct as an appendix to the trial protocol, and in signing the protocol, agree to support these ethical and scientific standards.

